5 STUDY POPULATION

5.1 Selection of the Study Population

Sample Size

We anticipate enrolling a total of 14,400 participants. We make no exclusions based on sex, age or race for enrolment, therefore we expect that our final enrolled study population will be roughly representative of those living within the study area.

These 14,400 will include:

- 1600 index cases in the routine contact investigation arm in Limpopo

- 1600 index cases in the routine contact investigation arm in Soshanguve and surrounding areas

- 800 index cases in the holiday contact investigation arm in Limpopo

- 800 index cases in the off-peak contact investigation arm in Soshanguve and surrounding areas

- 9,600 contacts (a mean of two contacts per case, accounting for some cases who will not have any contacts, based on our enrollment of household contacts in our recent trial in Limpopo)

Study Population Sources

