Index cases will represent a sample of consecutive consenting individuals diagnosed with pulmonary TB (including microbiological and/or chest x-ray diagnosis) from twelve hospitals in Vhembe and Capricorn Districts of Limpopo, and 33 primary health care clinics and two district hospitals in Soshanguve and surrounding areas. The only exclusion criteria will be a plan not to pursue treatment within the study district (as this would make contact investigation infeasible in the programmatic setting), and being on TB treatment for longer than one month (as these cases will likely be negative by liquid culture in order to identify transmission links between cases using whole genome sequencing). Note that contacts do not have the same requirement of planning to pursue treatment within the district; thus, it is possible - and expected - that holiday contact investigation in Limpopo will yield cases from outside the district, for example. Individuals who later decline to have contact investigation performed (or who, for example, provide false contact information thus making contact investigation infeasible) will still be included in the study sample and in the denominator for all analyses. Our aim is to make the population of this study as representative as possible as the target population for the proposed intervention. Eligible participants in the bioethics sub-study will include all individuals who were enrolled in the parent study and completed follow-up for the primary outcome (including those who declined or were ineligible to participate in household contact investigation). We will enroll consecutive eligible participants in each district until our desired sample size (64 evaluable index cases and 64 evaluable household contacts from each district) has been attained.

Eligibility Criteria

Subjects in each of the below participant categories must meet each eligibility criteria for that category:

TB index cases:

Inclusion criteria:

- Age 0-99 years (Including those recently deceased)
- Diagnosed with pulmonary TB at a study hospital or clinic (microbiological and/or chest x-ray diagnosis)

Exclusion criteria:

- Unwilling/unable to provide informed consent (including next of kin, for those recently deceased)
- Plan not to pursue TB treatment within the study district
- Unwilling/unable to comply with study procedures

Contacts:

Inclusion criteria:

- Age 0-99 years (18-99 for the bioethics sub-study)

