6 STUDY PROCEDURES/EVALUATIONS

6.1 Study Procedures

Recruitment

Within Limpopo Province, we will have two study sites, one in Vhembe and one in Capricorn district and these sites will recruit participants from a total 12 hospitals. In Tshwane (across both North West and Gauteng provinces) we will have one site in Soshanguve, and this will recruit participants from 33 clinics and two district hospitals. Within each site and clinic/hospital, we will seek to enroll all consecutive patients meeting the following inclusion criteria: (a) diagnosed with pulmonary TB at one of the study health facilities (including microbiological and/or chest x-ray diagnosis); (b) plan to pursue treatment within the study district; (c) willingness to provide informed consent and comply with study procedures. We will also include those patients who are recently deceased from the hospital register. Eligible participants will be identified by weekly review of the presumptive TB and TB treatment registers in each location, also in close collaboration with healthcare staff in each study health facility. We will approach all potentially eligible participants for informed consent at their treatment location within two weeks of diagnosis, making phone calls as necessary to contact participants who have been lost to follow-up between diagnosis and treatment initiation. For patients who are recently deceased, the next of kin will be contacted and asked if they can consent for the patient's information to be included in the study. Next of kin will also be asked to provide temporary consent for index patients who are too ill to consent at the time of enrollment. (These patients will be reapproached for consent once they have recovered to the extent of being able to complete the consent process.) After providing informed consent, participants will be randomized via a computer-generated algorithm to either routine or novel (holiday or off-peak) household contact investigation. Of note, participants who after consent and randomization, decline to accept household contact investigation - or who cannot be located at home at the time of home visit, will be included in the primary analysis as not resulting in a secondary case detected. Recruitment will be continued until 2400 participants are enrolled in each arm (expected to be completed within 28 months). For the bioethics sub-study, eligible participants will include all individuals who were enrolled in the parent study and completed follow-up for the primary outcome (including those who declined or were ineligible to participate in household contact investigation). For this sub-study, we will enroll consecutive eligible participants in each district until our desired sample size (~64 index cases and ~64 evaluable household contacts from each district) has been attained.

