7 STUDY SCHEDULE

7.1 Screening and Enrollment

Within Limpopo Province, we will have two study sites, one in Vhembe and one in Capricorn district, while in Tshwane municipality we will have one site covering Soshanguve and surrounding areas. Within each site, we will seek to enroll all consecutive patients meeting the eligibility criteria. Potential eligibility will be assessed weekly review of the presumptive TB and TB treatment registers at each study facility, in close collaboration with healthcare staff in each hospital. We will approach all potentially eligible participants for informed consent at their treatment location within two weeks of diagnosis, making phone calls and/or home visits as necessary to contact participants who have been lost to follow-up between diagnosis and treatment initiation.

All individuals present at the household at the time of a household study visit will be considered eligible for enrollment as contacts, and all adults approached during the timing of the bioethics sub-study will be considered eligible for enrollment into that sub-study.

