1. The TB prevalence ratio, comparing highly mobile to less mobile index patients, measuring mobility on two scales (neighborhood/intra-urban and regional/intra-national). For the former, we will estimate the number of kilometers traveled on a daily basis (secondary analysis: amount of time spent in transit), truncating long excursions at 50km (one hour). Based on exploratory data analysis and consideration of generalizable numbers (e.g., multiples of 5 and 10), we will consider a binary measurement of "highly mobile" versus "less highly mobile" at a natural break near the midpoint of the data. We will then use logbinomial regression to adjust for a priori potential confounders that will include age, sex, socioeconomic status, and HIV status, and robust variance estimation to account for clustering by households. Analyses will be stratified by site. We will perform a similar analysis for regional/intra-national mobility, taking as the primary exposure variable the self-reported number of trips per year greater than 50km (secondary analysis: number of nights spent away from primary residence). For each measure of mobility, we will explore additional methods of modeling the exposure variable, including continuous (linear), using restricted cubic splines (which may yield less interpretable estimates of effect but more flexible incorporation of complex patterns in the data), and as a categorical ("dummy variable") exposure – again at natural breaks in the data.

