- 5. Relative fidelity of each novel strategy using a process checklist for each index case and household, including whether the household visit was offered and accepted, whether the visit was attempted, whether the visit was successful (i.e., enrolled at least one contact), whether symptom screening and sputum collection were completed and whether newly identified TB cases were notified and referred for treatment. We will model fidelity as a binary outcome, using log-binomial regression, with the primary exposure of interest being novel versus standard contact investigation (separately in each setting), adjusting for potential confounders (for example, socio-demographic and clinical factors) and enrollment site as with the acceptability outcome and robust standard errors for multiple outcomes per household. Analyses will be stratified by site

- 6. Sustainability of each novel strategy will be accomplished by incorporating an indicator variable for the six-month time windows of the study period into the multivariable regression models of acceptability and fidelity outcomes described above, and evaluating for interactions between this time window indicator and the primary exposure variable (i.e. investigation arm).

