- 8. Experiences of inconvenience, attitudes toward confidentiality, motivation to participate, and preferences for disclosure. Outcome measures will be assessed via Likert scales which will be evaluated via multivariable regression, adjusting for demographic characteristics, district, study arm, and household characteristics (e.g., size). Responses will be dichotomized based on exploratory data analysis and conduct log-binomial regression, comparing these results to those of linear regression performed after assigning a numerical value to each response level. Our generic (e.g. unlabeled) discrete choice experiment (DCE) will be based on five different attributes (disclosure of index case TB status, routine vs off-peak evaluation, inclusion of routine HIV testing, use of official vs unmarked cars, provision of monetary reimbursement for time), each with two different levels. The DCE will utilize a fractional factorial design created to estimate the main effects alone. Results from the DCE for certain characteristics

will be compared against a double-bounded contingent valuation survey in which we will evaluate participants' willingness to accept household CI (with different characteristics) with and without monetary reimbursement of different levels (to compensate for household members' time).

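### The survey regressions for secondary outcome 8 name no allowance for household clustering; to the extent that respondents share a household, standard errors for arm, district and household size will be too small

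*Combined protocol and SAP*

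**What the plan says.** Secondary outcome 8 (Section 11.4) covers inconvenience, confidentiality, motivation and disclosure. It is measured on "Likert scales which will be evaluated via multivariable regression, adjusting for demographic characteristics, district, study arm, and household characteristics (e.g., size". Responses are to be dichotomized, and the analysts will "conduct log-binomial regression, comparing these results to those of linear regression performed after assigning a numerical value to each response level". No clustered variance, estimating-equation method or household random effect is named.

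Other analyses do deal with the household. Outcome 1 uses "robust variance estimation to account for clustering by households" and outcome 5 uses "robust standard errors for multiple outcomes per household". The adjusted regression for the primary outcome names clustering by household and enrolment site. Outcome 3 (Section 11.1) avoids the issue by questioning one randomly chosen person in each sampled household.

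On sampling, Section 5.1 says the bioethics sub-study will "enroll consecutive eligible participants in each district until our desired sample size (64 evaluable index cases and 64 evaluable household contacts" from each district, and Section 6.1 repeats the consecutive rule. Section 7.1 adds that "all adults approached during the timing of the bioethics sub-study will be considered eligible for enrollment into that sub-study". Home visits recruit every available household member (Section 6.1), and Section 5.1 expects "a mean of two contacts per case, accounting for some cases who will not have any contacts". No rule limits the survey to one person per household.

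**The concern.** People in one home share an index diagnosis and often the same visit, so their answers on stigma, inconvenience and disclosure are plausibly correlated. The index case is the unit randomized, so arm is the same for everyone in a household, as are district and household size. Adjusting for household size as a covariate does not remove the remaining within-household correlation.

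If the models are fitted as written, with ordinary model-based standard errors, any positive correlation makes the intervals for those three terms too narrow and their p-values too small. For a contrast within the household, such as index patient versus contact, the error runs the other way. At stake is the quantitative inference of the bioethics objective.

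**Working it through.** **The plan's own figure.** The documents give no power, standard error or intraclass correlation (ICC) for this survey. They do give its size, which reproduces two ways. Section 5.1: 3 districts × (64 + 64) = 384. Section 4: 300 surveys + 6 × 10 focus-group participants + 24 interviews = 384. Both agree with the 384 (192 index cases and 192 contacts) in Section 11.3. The regressions therefore rest on about 300 respondents. With equal representation by role and district (Section 4), that is 300 / 6 = 50 index cases and 50 contacts per district.

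**Assumed inputs.** The ICC is taken as 0.1 to 0.3. The overlap of respondents within households is also assumed, in three patterns that respect the equal quotas:

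- A: 300 different households.
- B: 150 households, each giving one index case and one contact.
- C: 75 households of three (one index case, two contacts) plus 75 index-only respondents. This gives 150 index cases and 150 contacts.

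**Formulas**, for a term constant within household:

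- Weighted cluster size m_w = Σm² / Σm. A: 1. B: (150 × 4) / 300 = 2. C: (75 × 9 + 75 × 1) / 300 = 2.5.
- Design effect DE = 1 + (m_w − 1) × ICC.
- Shortfall of the independence standard error = 1 − 1/√DE.
- True error of a nominal 5% test = 2 × (1 − Φ(1.96/√DE)).

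| Pattern | ICC | DE | SE too small by | True test error |
|---|---|---|---|---|
| A | any | 1.00 | 0% | 5.0% |
| B | 0.1 | 1.10 | 4.7% | 6.2% |
| B | 0.3 | 1.30 | 12.3% | 8.6% |
| C | 0.1 | 1.15 | 6.7% | 6.8% |
| C | 0.3 | 1.45 | 17.0% | 10.4% |

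In effective sample size, the 300 respondents are worth 300/1.30 = 231 under B and 300/1.45 = 207 under C at ICC 0.3.

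**Simulation check.** Pattern C was simulated with arm allocated 2:1 by household, a linear model with arm and role as terms, and 2,000 runs per ICC.

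| ICC | Arm: true SD / independence SE | Test error, independence SE | Test error, household-clustered SE | Index vs contact: true SD / independence SE |
|---|---|---|---|---|
| 0.1 | 1.09 | 6.4% | 5.0% | 0.97 |
| 0.3 | 1.21 | 10.6% | 5.7% | 0.91 |

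The simulation agrees with the formula for arm, shows that clustered errors largely restore the 5% level with 150 households, and confirms the reversal for the index-versus-contact contrast. It covered the linear model only. For the log-binomial model the same formula applies, with the ICC taken on the binary response.

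**The case against.** Much of the case on the other side stands.

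- **Silence is not a statement.** A reader might infer that the plan declares respondents independent. It does not; it names no variance method for these models. The gap is one of specification, seen by contrast with neighbouring items.
- **Household overlap is inferred.** No passage says how many respondents come from one home. The mean of two contacts covers all ages, while the sub-study takes adults only. Index cases who declined household investigation are eligible and may bring no contacts. Recently deceased index cases are in the parent study but cannot answer a survey. Clusters may therefore be smaller than in B or C.
- **The ICC is assumed.** What matters is the correlation left after adjustment for district, arm and household characteristics, which may be lower than 0.1–0.3.
- **Three respondents in every household does not fit.** A reader might take one index case plus two contacts throughout, giving DE = 1 + 2 × 0.3 = 1.6, a 21% shortfall and 12% test error. That would be a 1:2 split, whereas Sections 4, 5.1 and 11.3 require equal numbers. On the two-contact premise, C is the fitting case.
- **Arm and district are adjustment terms.** The bioethics objective in Section 3 is mainly descriptive and names no arm or district comparison, and no power is stated for one.

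These points limit the size and importance of the problem. They do not remove it: consecutive enrolment with no one-per-household rule makes shared households very likely, and the plan already treats household clustering as needing correction elsewhere.

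**Conclusion.** The point holds in a limited form. The outcome 8 log-binomial and linear regressions lack the household correction that other analyses in Section 11.4 carry. If respondents share households and their answers are positively correlated, independence standard errors are too small for arm, district and household size. Over the assumed ICC range of 0.1–0.3, the shortfall is 5–12% under B and 7–17% under C; it is nil if no households are shared. It would be wrong to conclude that every standard error in these models is too small, because the index-versus-contact contrast errs in the opposite direction. It would also be wrong to carry the concern over to the primary outcome, which this omission does not touch. No magnitude is claimed for the choice-experiment or contingent-valuation models: Section 11.4 states no estimator for them and none was computed here.

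**What to change.** Add one clause to Section 11.4, secondary outcome 8: the log-binomial and linear survey models use standard errors clustered on household. Keep a coded, non-identifying household ID on each survey record. Section 7.3 says that no personal identifiers are recorded at the sub-study visit, so without such a link the correction may not be possible later. A coded ID is compatible with that rule and with the coded study IDs in Section 14.5. The choice-experiment and contingent-valuation models may use the same clustering, which would also cover repeated answers from one respondent.

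The cost is a sentence, one coded field and slightly wider intervals for household-level terms. If clustering was intended all along, writing it down changes nothing.

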11.5 Blinding

The US-based PI ([name]), the South African-based co-PIs ([name] and [name]) and NIH sponsors will be blinded to all primary and secondary outcomes during conduct of the study through the completion of data cleaning and analysis.

12 ACCESS TO SOURCE DATA/DOCUMENTS

Research records for this study will be kept in a centralized study office in each district, in compliance with Section 4.9 of ICH E6 GCP, and regulatory and institutional requirements for the protection of confidentiality of subjects. As part of participating in a DMID-funded, study, each site will permit authorized representatives of the funder, DMID, and regulatory agencies to examine (and when required by applicable law, to copy) clinical records for the purposes of quality assurance reviews, audits and evaluation of the study safety and progress.

13 QUALITY CONTROL AND QUALITY ASSURANCE

Details on all quality control and quality assurance procedures can be found in the associated DMID approved Clinical Quality Management Plan. The participating site is responsible for conducting routine quality assurance (QA) and quality control (QC) activities to internally monitor study progress and protocol compliance. The site principal investigator will provide direct access to all study-related sites, source data/data collection forms, and reports for the purpose of monitoring and auditing by the sponsor, and inspection by local and regulatory authorities. The site principal investigator will ensure all study personnel are appropriately trained and applicable documentations are maintained on site.

The data management center will be maintained by PHRU with input from Setshaba Research Centre, and will implement quality control procedures beginning with the data entry system and generate data quality control checks that will be run on the database within 2 days of mobile data capture. Cyclical queries will be communicated to the sites for clarification and resolution.

Protocol compliance will be managed on a day-to-day basis by the study coordinator, and overseen by the PI and other study investigators. The study coordinator will ensure proper training on study protocol of all study staff and will conduct routine field visits in order to monitor study compliance. Data quality will be monitored for missing values on a weekly basis by the study coordinator who will review case report forms and remediate errors or omissions with study staff. In depth data quality checks will be made on a quarterly basis, managed by the data manager.

A study monitor from PHRU will make periodic field visits to study sites to review study practices and documents in order to ensure compliance with ethical standards.

14 ETHICS/PROTECTION OF HUMAN SUBJECTS

14.1 Declaration of Helsinki

The investigator will ensure that this study is conducted in full conformity with the current revision of the Declaration of Helsinki, or with the International Conference for Harmonisation Good Clinical Practice (ICH-GCP) regulations and guidelines, whichever affords the greater protection to the subject.

14.2 Institutional Review Board

Independent ethics review of this study will be handled in South Africa by the Human Research Ethics Committee at the University of the Witwatersrand, which holds a current U.S. Federal-Wide Assurance issued by OHRP, and in the United States by the Institutional Review Board at the Johns Hopkins Bloomberg School of Public Health.

14.3 Informed Consent Process

Written consent (and assent)

Written consent will be obtained for all study participants. For children, written consent will first be obtained from the parent/guardian and followed with written assent from children 7 years and older. Consent will be conducted privately and one-on-one. Consent will be obtained using an easily-understood form (as the educational level of the target population is low). Risks and benefits of participation will be explained, with a clear alternative of no participation, and participants will be clearly informed that consent can be withdrawn at any time without adverse effects on their clinical care. Informed consent will be provided in the participant's preferred language, including English and four local languages (Tshivenda, Sepedi, Tsonga and Setswana). Our experience in Limpopo Province is that, while a number of local dialects are spoken, almost all participants can communicate fluently in one of these languages. All informed consent documents, including a register thereof, will be maintained in a locked cabinet accessible only to study personnel. We anticipate that some of the participants are not literate, and hence not able to read the written consent. For such participants, we will read the consent document as described above, asking participants to make a mark on a corresponding form (and a witness who is not a member of the study staff to sign the form) after having the opportunity to ask any questions and being given the opportunity to decline enrollment with no adverse consequences on their clinical care. Enrollment of illiterate participants will be important to for proper representation of the study population. For these individuals, again, the scientific benefit increases if we are able to include all potential participants (not only those whom we

could consent with on-site staff), and this activity of screening for TB is already the existing standard of care.

14.3.1 Informed Consent/Assent Process (in Case of a Minor or others unable to consent for themselves)

In the case of minors, aged 7-18 years, we will seek written assent, using a separate form from that used for adults. The assent forms will be written in simpler language the details of the study, study procedures and risks. In addition, we will seek parent/guardian informed consent for the participation of these minors. For children <7 years, we will seek only parental informed consent.

